This is a pilot study designed to determine study feasibility and evaluate the impact of a novel intervention, MORE, on opioid use and chronic pain among individuals receiving methadone maintenance treatment. We will evaluate progression to a larger study based on the success of three key milestones. For the pilot study, we plan to evaluate our ability to recruit participants into the study, defining successful recruitment as 75% or more of our planned sample size by month 7. Retention will be considered successful if 50% of participants attend at least 4 MORE sessions, and will be assessed at month 9. We will evaluate our ability to collect 8-week and 16-week follow up data, defining success as a follow-up rate of 65% of participants at 8-weeks and 50% of participants at 16-weeks assessed at month 11. In addition to evaluating study feasibility through obtaining these milestones, we will obtain information about the efficacy of MORE on opioid use and chronic pain among MMT patients. It is hypothesized that: 1) Participants in MORE will have a longer duration of time to first opioid lapse than TAU participants; 2) Participants in MORE will have a longer duration of time to MMT dropout than TAU

participants; 3) At 8 and 16 –weeks post-enrollment, the MORE group will have fewer days of opioid use and fewer days of any drug use; 4) At 8 and 16 –weeks post-enrollment, the MORE group will have more days of methadone treatment than the TAU group; and 5) At 8 and 16 –weeks post-enrollment, the MORE group will have greater decreases in pain severity and pain interference than the TAU group.

1.2 Research Significance (*Briefly describe the following in 500 words or less*):

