1.3 Research Design and Methods

This pilot study is a 2-arm individually randomized controlled trial design in which outcomes of MMT patients randomized to MORE are compared to outcomes of those randomized to treatment as usual (TAU). In the pilot study (R21; N=31), we will randomize MMT patients with chronic pain to MORE (n=15) or TAU (n=16). This study phase will focus on establishing study feasibility in recruiting, retaining, and following up study participants before progressing to a larger Phase II clinical trial (R33, N=150). Participants with pain who are receiving MMT for an opioid use disorder (OUD) will be recruited from the New Brunswick Counseling Center (NBCC) and the Lennard Clinic.

A. *Describe, in order of occurrence, all research procedures being performed, when and where they are performed, and by whom (including procedures being performed to monitor subjects for safety or minimize risks).*

Participants will be recruited through flyers posted in the clinics, being approached by research assistants in the waiting room of their usual methadone clinic (New Brunswick Counseling Center or Lennard Clinic), and referral by clinic staff. The number of individuals who contact the study staff through the flyers or referral and who are approached by study staff in the clinics will be tracked. Number of individuals who refuse study participation and who consent to the study will also be tracked. If an individual is interested in study participation, a trained research assistant will lead the individual through the informed consent process in a private space.

Participants randomized to the MORE condition will participate in eight, weekly, two-hour group sessions led by a clinic or study counselor. Each session will contain 4-8 participants and take place in a private room at the New Brunswick Counseling Center (NBCC) or the Lennard Clinic. Attendance at each session and reasons for missing sessions will be recorded. Participants randomized to the control condition will continue receiving treatment as usual at the NBCC.

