All study participants will partake in a total of three interviews lasting up to 90 minutes and occurring at baseline, 8- and 16- weeks post-baseline in a private room at NBCC or the Lennard Clinic. Each participant will also have a urine or saliva sample collected during each assessment. This is required to verify self-report of drug use. Due to social desirability, it is common for people to not accurately report drug use; therefore, biochemical verification is the gold standard measure of drug use. All attempts to reach participants to schedule follow-up assessments will be tracked. Participants will also complete cognitive testing (for approx. 30-45 minutes) at baseline and 8-weeks and ecological momentary assessments (EMA) conducted via smartphones, which will be provided to each participant by study staff. EMA participation will require the participant to respond to twice-daily prompts in which they will be asked a series of brief questions regarding their current mood and exposure to opioid triggers. Additionally, subjects will be asked to initiate responses when they experience serious craving or relapse to opioid use. Each EMA assessment will last approximately 3-5 minutes.

B. What data points will be collected including long-term follow-up?

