6.3 Data and Safety Monitoring

A. Periodic Data Evaluation

Describe the plan to periodically evaluate the data collected regarding both harms and benefits to determine whether subjects remain safe. The plan might include establishing a data monitoring committee and a plan for reporting data monitoring committee findings to the IRB and the sponsor.

The Data and Safety Monitoring Board (DSMB) will meet every 3 months to monitor and evaluate the safety of participants throughout the course of the research study. The DSMB will:

- Assess the performance of the study with respect to participant recruitment, retention and follow-up, protocol adherence, and data quality and completeness.
- Monitor interim data regarding the safety of the study regimes.
- Review and consider any protocol modifications or ancillary studies proposed by study investigators after the main trial begins to ensure that these do not negatively impact on the main trial.
- Advise the Institutional Review Board as to whether the protocol should continue as scheduled or undergo a modification due to a finding from the monitoring process.

B. Type of Data Evaluated

Include what data are reviewed, including safety data, untoward events, and efficacy data.

The study investigators and the DSMB will be responsible for data safety and monitoring. Quarterly, the DSMB and the investigators will monitor the cumulative safety data during the period when participants are in the study. They will: 1) assess the performance of the study with respect to participant recruitment, retention and follow-up, protocol adherence, and data quality and completeness, to help ensure the likelihood of successful and timely trial completion; 2) monitor interim data regarding the safety of the study regimens; 3) review and consider any protocol modifications by the study investigators after the trial begins to ensure that these do not negatively impact on the study; and 4) advise the Institutional Review Board and NIH as to whether the protocol should continue as scheduled or undergo a modification due to a finding from the monitoring process.

C. Collection of Safety Information

Explain how the safety information will be collected (e.g., with case report forms, at study visits, by telephone calls with participants).

Safety information will be collected during participant's assessments, telephone calls with participants, conversations with clinic staff, and MORE group sessions.

D. Frequency of Data Collection

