The frequency of data collection, including when safety data collection starts.

Safety data collection will begin with collection of the first baseline assessment and continue through the end of the follow-up data collection period (12 months total). In addition to using assessment data to monitor safety, study clinicians will record any adverse events that they become aware of during MORE group sessions and study Investigators will ask NBCC and the Lennard Clinic personnel, with participant consent, to notify the research team should they become aware that any study participant has been hospitalized or experienced any other adverse event. Such notifications will be requested throughout the study period. All adverse events will be recorded on spreadsheets and will include details of the adverse event and whether or not it was study-related. Numbers and types of events and other quantifiable event details will be entered into a database for analysis.

E. Reviewer of Data

Who will review the data?

The DSMB will meet on a quarterly basis to monitor the cumulative safety data during the period when participants are in the study. The DSMB will monitor the study according to the guidelines specified in the study protocol and the operating procedures established at the initial DSMB meeting, unless the DSMB determines during the course of the trial that modification of the guidelines is in the best interest of the study and its participants. Such a decision may be based on new information that emerges during the course of the study (e.g., publication of the results of a similar study), realization of inappropriate initial study assumptions, or the occurrence of an unanticipated scenario.

F. Schedule of Review of Cumulative Data

The frequency or periodicity of review of cumulative data.

Under supervision of the investigators, the Research Assistant will conduct monthly descriptive summaries on all data to ensure their accuracy. This will not involve completing any statistical comparisons. If problems are noted in data entry (e.g., out of range values, missing values), the Research Assistant and the investigators will investigate the root cause, and solutions to rectify the problem.

G. Tests for Safety Data

The statistical tests for analyzing the safety data to determine whether harm is occurring.

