Basic statistical tests, including frequency distributions, Anovas and t-tests, will be carried out to compare the control and intervention groups on numbers and types of adverse events within specific time frames in order to insure the safety of the intervention.

H. Suspension of Research

Any conditions that trigger an immediate suspension of the research.

Considering the minimal risk nature of the intervention, we do not anticipate any serious adverse events that could trigger the immediate suspension of the research.

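### The between-arm adverse event comparison pools sources open to both arms with one that only MORE has, so MORE counts would tend to run higher even at equal risk

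*Combined protocol and SAP*

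**What the plan says.** Section 6.3 C lists four sources of safety information: participant assessments, followed by "telephone calls with participants, conversations with clinic staff, and MORE group sessions". Section 6.3 D adds: "In addition to using assessment data to monitor safety, study clinicians will record any adverse events that they become aware of during MORE group sessions". It also asks personnel at both clinics to notify the team, with participant consent, if they learn that "any study participant has been hospitalized or experienced any other adverse event".

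The events go into one record: "All adverse events will be recorded on spreadsheets and will include details of the adverse event", together with study-relatedness. Numbers, types and other quantifiable details are then entered into a database. The source of the report is not among the fields named. Section 6.3 G applies frequencies, ANOVA and t-tests to that record, with this stated purpose: "compare the control and intervention groups on numbers and types of adverse events within specific time frames in order to insure the safety".

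Section 1.3 A sets the contact schedule. MORE has "eight, weekly, two-hour group sessions led by a clinic or study counselor. Each session will contain 4-8 participants". For both arms, "All study participants will partake in a total of three interviews lasting up to 90 minutes", at baseline and at 8 and 16 weeks.

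Section 1.9 B has a depression scale and an anxiety scale completed at every research visit in both arms.

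**The concern.** A comparison of event counts is like-for-like only if an event has the same chance of being recorded in each arm. Here three channels serve both arms and a fourth, the weekly group session, serves MORE alone. Counseling at the methadone clinic does not restore the balance, because MORE participants remain clinic patients and have that channel too.

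If true risk is equal, the extra channel can only add MORE events. An excess in MORE would then be hard to separate from closer observation, both in the DSMB's quarterly review and in the final report. If the planned larger trial (N=150) reuses the safety section, it inherits the same feature. Source is easy to note when an event is logged and hard to reconstruct later.

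**Working it through.** The plan states no adverse event rate, capture rate or safety threshold, so it has no figure to reproduce. The check shows the direction, and then a size under stated assumptions.

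**Which source covers which arm (6.3 C and D)**

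| Source | MORE | TAU |
|---|---|---|
| Assessments | yes | yes |
| Telephone calls | yes | yes |
| Clinic staff | yes | yes |
| MORE group sessions | yes | no |

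**Expected count ratio at equal true risk**

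Inputs:
- c = proportion of events caught by shared sources, the same in both arms. Assumed 0.5 to 0.8.
- s = proportion of the remaining events that sessions catch in the weeks when they run, allowing for imperfect attendance. Assumed 0.25 to 0.50.
- w = share of follow-up covered by sessions = 8/16 = 0.5 (sections 1.3 A and C), with events assumed to be spread evenly over time.

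Recorded fraction in TAU = c. Recorded fraction in MORE = c + (1 − c) × w × s. The ratio per participant is the second divided by the first.

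| c | s | MORE fraction | Ratio |
|---|---|---|---|
| 0.8 | 0.25 | 0.8 + 0.2 × 0.5 × 0.25 = 0.825 | 1.03 |
| 0.8 | 0.50 | 0.8 + 0.2 × 0.5 × 0.50 = 0.850 | 1.06 |
| 0.5 | 0.25 | 0.5 + 0.5 × 0.5 × 0.25 = 0.5625 | 1.13 |
| 0.5 | 0.50 | 0.5 + 0.5 × 0.5 × 0.50 = 0.625 | 1.25 |

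**What a t-test would show**

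Poisson counts were simulated with equal true rates, 15 v 16 participants and the same 8-of-16-week limit (20,000 runs per setting). With an assumed 2 events per participant, c = 0.5 and s = 0.5, MORE had the higher mean in 74% of trials and p < 0.05 occurred in 9%. With 1 event per participant the figures were 67% and 7%. Over a wider assumed range (c 0.3 to 0.7, s 0.2 to 0.8) the ratio ran from 1.04 to 1.93 and p < 0.05 occurred in 5% to 36% of trials. The direction is the same throughout; the size depends on the assumptions.

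**Effect of restricting to shared sources**

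If session findings never reach a shared source, both fractions equal c and the ratio is 1.00. If half of the session-only events are relayed to clinic staff and counted as shared (assumption), half of the excess returns: 1 + 0.031/2 = 1.02 up to 1 + 0.25/2 = 1.13. The restricted comparison therefore needs a rule for relayed reports.

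**The case against.** **The pooled count errs on the safe side.** Section 4.9 A names discomfort in assessments and group sessions as the main risk, and the session content in section 1.6 A includes imaginal stress exposure and imaginal opioid cue exposure. Harm provoked by a session can arise only in MORE and may be seen only there. Replacing the pooled comparison with a shared-source one could hide real harm. This stands, and it is why the all-event comparison should stay.

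**Shared sources are not cleanly separate.** A clinic counselor may lead the group (1.3 A), and sections 4.9 A and E allow harm concerns raised in sessions to reach clinic staff. This also stands, and the fix has to handle it.

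**The plan may already allow source to be recorded.** Section 6.3 D records event details and study-relatedness, and a manual of procedures is promised. Source could be entered there, but no text requires it, and 6.3 G does not use it.

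**Stronger readings that the documents do not support.**
- A reader might infer that sessions add capture throughout follow-up. Without the 8-week limit, the same inputs give 1.06 to 1.50, but sessions cover only about half of the 16 weeks.
- A reader might set 2 scheduled TAU contacts after baseline against up to 10 in MORE (2 interviews plus 8 sessions). That leaves out twice-daily EMA prompts and clinic attendance, which both arms have.
- A reader might infer that the depression and anxiety scales have no tie to safety. Section 6.3 D uses assessment data to monitor safety. Section 4.9 E starts a written protocol when thoughts of harm appear on study measures, and 4.9 A makes new or worsening risk of harm an adverse event. What remains is narrower: section 6.3 does not name the two scales, they have no worsening cut-off, and they are not in the 6.3 G tests. Section 6.1 A already allows exploratory group comparisons.

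**Conclusion.** The point holds for event counts. As written, the comparison mixes shared sources with a MORE-only source, and at equal true risk MORE would tend to show more recorded events: about 1.03 to 1.25 times TAU per participant. That range rests on assumed capture rates, evenly spread events and session capture limited to half of follow-up. The direction does not depend on the particular rates, provided that sessions catch at least some events that the shared sources miss.

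The consequence is modest. This is a 31-person pilot declared unpowered (6.1 B), the milestones in 1.1 B concern recruitment, retention and follow-up, and the likely error is to make MORE look worse rather than to conceal harm. It is a low-severity improvement in how safety is reported.

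**What to change.** **Adverse event spreadsheet (6.3 D).** Add every source that reported each event and which source was first. Treat a session leader's report, or a clinic-staff report relayed from a session, as session-sourced.

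**Section 6.3 G.**
1. Keep the comparison of all events.
2. Add a comparison restricted to events independently reported by a source open to both arms: assessment, telephone call or clinic staff. An event seen in a session and also independently reported by one of these stays in.
3. List session-only events separately as possible intervention-related harm.

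**Optional.** Tabulate the depression and anxiety scales by arm at weeks 8 and 16 as descriptive safety data. Precision would be low. The 95% half-width, t × √(1/n₁ + 1/n₂), is 0.74 SD with full data (15 v 16) and 1.07 SD at the 50% week-16 benchmark if follow-up is equal in both arms (8 v 8), before any baseline adjustment or allowance for clustering within MORE groups. Such a table cannot show that MORE is safe.

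**Cost.** One extra column and a second table, with a few sentences in 6.3 G; no new visits or measures. The restricted comparison can miss harm seen only in sessions, so it supplements the all-event comparison and does not replace it.

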6.4 Reporting Results

A. Sharing of Results with Subjects

Participants will be provided with the study PI's name and contact information along with an estimate of when the study results will be available. Participants may contact the PI should they be interested in obtaining results of the study.

B. Individual Results

N/A

C. Aggregate Results

As noted above, subjects will be given the PI's name and contact information and encouraged to follow-up with the PI should they be interested in obtaining results of the study.

D. Professional Reporting

Study results will be described in reports to the funding agency and published in peer-reviewed journals. Findings may also be presented at professional meetings.

6.5 Data Sharing

Analyses of data generated from this project will be shared with the scientific community through publications in peer-reviewed journals and presentations at scientific meetings. Because we will be following study participants, we will be collecting identifying information. Even though the final dataset will be stripped of identifiers prior to

release for sharing, we believe that there remains the possibility of deductive disclosure of participants with unusual characteristics. Thus, we will make the data and associated documentation available to research community scientists only under a data-sharing agreement that provides for: 1) a commitment to using the data only for research purposes and not to identify any individual participant; 2) a commitment to securing the data using appropriate computer technology; and 3) a commitment to destroying or returning the data after analyses are completed. The study will be registered with clinicaltrials.gov

7.0 Data and/or Specimen Banking

N/A

8.0 Other Approvals/Authorizations

Describe any approvals that will be obtained prior to commencing the research. (E.g., school site authorization, data use agreements, external site authorization, funding agency, Bio-Safety, Radiation -Safety etc.)

N/A

